3.10 PD and PK/PD analyses

Exposure-Response analysis

- The following are objectives for exposure-response analysisCharacterize the exposure-efficacy relationship of ruxolitinib with efficacy response defined as overall response rate at Day 28, durable response at Day 56, and Overall survival. Exposure metrics may be described in further details in a separate analysis plan.
- Characterize the exposure-safety relationship of ruxolitinib with safety response defined as 1st occurrence AEs, 1st occurrence of G3/4 AEs, 1st occurrence of AEs of interest, and appropriate liver function parameters. Exposure metrics may be described in further details in a separate analysis SAP.
- Exposure-Biomarker – [REDACTED]

For overall survival, if sufficient events have accrued (i.e., at analysis time points after the primary analysis), a Cox regression model with appropriate patient demographic and prognostic factors as covariates and the log-trough concentration level as a time dependent covariate will be fitted as appropriate. Goodness of fit of the model will also be examined, and other exposure measures (such as dose intensity) may be considered if appropriate. The survival time should be calculated from the time of first dose. The hazard ratio and 95% confidence interval for a

decrease by half in exposure will be displayed if appropriate. Kaplan-Meier curves may be used to summarize the data based on relevant quantiles of PK.

[figure not shown]
For incidence of specific AEs, Day 28 response and Day 56 durable response, logistic regression models for efficacy may be used including log- time-averaged trough concentration, and log-trough concentration (last observed prior to onset of event) for safety, as well as other demographic and prognostic covariates in the model as appropriate. The average trough concentration included in the model for Day 28 response will be the geometric mean of the Day 7, Day 14, Day 21 and Day 28 adjusted trough concentration. A similar average trough concentration will be calculated for the Day 56 response except the Day 42 and Day 56 will also be included. Goodness of fit of the model will also be examined, and other exposure measures (such as dose intensity) may be considered if appropriate. The odds ratio and its 95% confidence interval for a two-fold increase in exposure will be displayed as appropriate.

[figure not shown]
Expected steady-state exposures and/or other PK parameters for the population may be computed by the population PK model accounting for dose modifications or dose interruptions up to the day prior to the day of assessments. Population PK derived parameters may be also considered for exposure-response analyses by appropriate methods.

[figure not shown]

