If the Phase I preliminary dose is different to RP2D, PK data will be listed and summarized by age group and dose level.

Population PK approach on pooled Phase I and Phase II data

Concentration results from the sparse sampling performed in the Phase II will be added to those from Phase I and analyzed further using nonlinear mixed effects modeling (population PK) or other model-based approaches, as appropriate. Details of the analysis method will be developed in a PK analysis plan and the population PK analysis will be documented in a separate report.

During modeling of the pharmacokinetics of study treatment, the broad principles outlined in the FDA guidance will be followed (Guidance for Industry: Population Pharmacokinetics Fed 1999).

Exposure-Response analysis

A detailed description of exposure-response analysis will be developed in the analysis plan. Briefly, the objectives are to:

[figure not shown]
- Characterize the exposure-efficacy relationship of ruxolitinib with efficacy response defined as overall response rate at Day 28, durable response at Day 56, and Overall survival. Exposure metrics will be described in further details in the analysis plan.
- Characterize the exposure-safety relationship of ruxolitinib with safety response defined as 1st occurrence AEs, 1st occurrence of G3/4 AEs, 1st occurrence of AEs of interest, and appropriate liver function parameters. Exposure metrics will be described in further details in the SAP.
- Exposure-Biomarker – [REDACTED]

[figure not shown]
Average steady-state exposures and/or other PK parameters for the population may be computed by the population PK model accounting for dose modifications or dose interruptions up to the day prior to the day of assessments. Population PK derived parameters may be used for exposure-response analysis by appropriate methods.

Data handling principles

Plasma concentration values below the limit of quantification (BLQ) will be set to zero by the Bioanalyst, and will be displayed as zero in the listings and flagged. BLQ values will be treated as zero in any calculations of summary statistics, and treated as missing for the calculation of the geometric means and their coefficient of variation (CV%).

Any missing PK parameter or concentration will not be imputed.

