3.2 Analysis sets

If the starting dose is different from the assigned dose level due to co-administration of ruxolitinib with strong CYP3A4 or dual CYP3A4/CYP2C9 inhibitors, these patients will be included under the assigned dose level and considered that they have received the full assigned dose. This applies to all analysis sets described below.

The **Full Analysis Set** (FAS) comprises all patients to whom study treatment has been assigned and who received at least one dose of study treatment. Patients will be analyzed according to the treatment they have been assigned to.

The **Safety Set** includes all patients who received at least one dose of study treatment. Patients will be analyzed according to the study treatment received, where treatment received is defined as the assigned dose level of ruxolitinib if the patient took at least one dose of that treatment or the first dose level received if the assigned dose level was never received.

The **Pharmacokinetic Analysis Set** (PAS) includes all patients who provide at least one evaluable PK concentration. For a concentration to be evaluable, patients are required to:

- Take the dose of ruxolitinib prior to PK sample.
- For pre-dose samples, do not vomit within 2 hours after the previous dosing of ruxolitinib prior to sampling; for post-dose samples, do not vomit within 2 hours after the dosing of ruxolitinib.

The PAS will be used for Non-compartmental analysis (NCA) for patients where extensive PK sampling is obtained. This analysis set will also be used for any exposure-response analysis

The **Efficacy Eevaluable Set** (EES) comprises all patients to whom study treatment has been assigned at the Recommended Phase 2 dose (RP2D) of ruxolitinib and who received at least one dose of study treatment at that dose level. If the starting dose is different from the RP2D due to co-administration of ruxolitinib with strong CYP3A4 or dual CYP3A4/CYP2C9 inhibitors, these patients will be included in the EES.

All statistical analysis and data presentation for all analysis sets will exclude any data collected but not required as per study protocol. Data with a Protocol Deviation Code OTH11 (Other GCP deviation- Additional samples or Data collected not required as per protocol) will not be part of the analysis data or any output presentation.

Any patients who withdrew Informed Consent or from whom written Informed Consent was not obtained (Protocol Deviation INCL01) will be excluded from all analyses sets.

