3.9 Pharmacokinetic endpoints

Pharmacokinetic Analysis Set (PAS) will be used in all pharmacokinetic data analysis and PK summary statistics.

In patients with extensive PK sampling on Day 1 (samples 1 to 8 described in [Section 8.6.1.1 of the protocol](#)), PK parameters of ruxolitinib will be calculated by non-compartmental methods using Phoenix WinNonlin (Pharsight, Mountain View, CA) software. The following parameters will be calculated ([Table 2-5](#)). Additional PK parameters may be estimated as needed.

Table 3-5 Non-compartmental pharmacokinetic parameters of ruxolitinib

AUClast	The AUC from time zero to the last measurable concentration sampling time (Tlast)
AUCinf	The AUC from time zero extrapolated to infinity
AUC0-12	The AUC from time zero extrapolated to 12 hours
Cmax	The maximum (peak) observed plasma drug concentration
Ctrough	The minimum observed plasma concentration at the end of an administration interval (corresponding to the pre-dose concentration prior to the following administration)
Tmax	The time to reach maximum (peak) plasma, blood, serum, or other body fluid drug concentration after single dose administration (time)
T1/2	The elimination half-life associated with the terminal slope (Lambda_z) of a semi logarithmic concentration-time curve
CL/F	The total body clearance of drug from the plasma
Vz/F	The apparent volume of distribution during terminal phase (associated with Lambda_z)

All plasma concentrations will be analyzed using a population PK approach.

Statistical methods for pharmacokinetic analyses

All individual plasma ruxolitinib concentrations data will be listed by group. Descriptive summary statistics will be provided by group at each scheduled time point. Summary statistics will include n (number of patients with non-missing values), mean (arithmetic and geometric), SD, CV (arithmetic and geometric), median, minimum and maximum. Individual profiles with median by dose level as well as arithmetic mean with SD and geometric mean ruxolitinib plasma concentration versus time profiles by treatment will be displayed graphically.

Ruxolitinib plasma PK parameters data will be listed by group. Descriptive statistics (n, arithmetic mean, standard deviation (SD), coefficient of variation (CV)% for mean, geometric mean, geometric CV%, median, minimum and maximum) will be provided for all PK parameters by dose level except for Tmax where median, minimum and maximum will be presented.

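### SAP 3.10 builds its Day 28 and Day 56 exposure metrics on Day 21 and Day 42 troughs that no PK schedule collects, and averaging the troughs that do exist would give metrics that differ by sampling schedule

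*SAP*

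**What the plan says.** SAP 3.10 makes the response models optional: "logistic regression models for efficacy may be used including log- time-averaged trough concentration". Its definition of the covariate is not optional. For Day 28 response it is the "geometric mean of the Day 7, Day 14, Day 21 and Day 28 adjusted trough concentration". For Day 56 durable response a similar average is used, "except the Day 42 and Day 56 will also be included". The word adjusted is not explained in the visible text.

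The same section leaves room for other choices. It allows other exposure measures, with dose intensity as an example, and population-PK exposures "accounting for dose modifications or dose interruptions up to the day prior to the day of assessments". It also says "Exposure metrics may be described in further details in a separate analysis plan". Protocol 12.5.4 is firmer about further detail: "A detailed description of exposure-response analysis will be developed in the analysis plan". The SAP introduction mentions that some PK analyses go to a separate SAP and report, without saying which.

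SAP 3.9 states that missing PK values are not imputed, and also that "All plasma concentrations will be analyzed using a population PK approach". On the PK analysis set, SAP 3.2 says "This analysis set will also be used for any exposure-response analysis".

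**The concern.** PK/PD relationships are a listed secondary objective, and the two trough averages are the only exposure metrics that SAP 3.10 defines concretely for the Day 28 and Day 56 models. A definition that needs uncollected samples has to be replaced by something else at analysis, and the SAP does not say what.

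The obvious substitute is to average whatever troughs a patient has. That brings two problems:

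- The covariate would mean different things under different schedules, and schedule is tied to phase, age group and enrolment order. An apparent exposure effect could then partly reflect those factors.
- Availability is tied to outcome. Protocol 6.1.5 and 9.1.1 require patients with lack of response at Day 28 to stop ruxolitinib. A sparse-sampled patient would therefore generally have a Day 56 on-treatment trough only after responding at Day 28, which is itself a condition for durable response. The number of troughs averaged would carry information about the outcome being modelled.

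**Working it through.** **Inputs.** Days required come from SAP 3.10. Pre-dose days and volumes come from Protocol Tables 8-5, 8-6 and 8-7. The Day 1 pre-dose sample precedes the first dose, so it is not a trough. The PK row of Table 8-1 refers back to 8.6.1.1 and adds no day.

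**Step 1: are the schedule tables complete?** Multiply the number of samples by 1.2 mL and compare with each table's stated maximum.

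| Schedule | Patients | On-treatment pre-dose days | Volume | Stated maximum |
|---|---|---|---|---|
| 8-5, extensive | about the first 5 of Group 1; Phase I of Groups 2 and 3 | 7, 14, 28 | 14 × 1.2 = 16.8 mL | about 17 mL |
| 8-6 | Group 4 | 7, 14, 28 | 7 × 1.2 = 8.4 mL | about 9 mL |
| 8-7, sparse | rest of Group 1; Phase II of Groups 2 and 3 | 28, 56, 84, 140, 168 | 10 × 1.2 = 12.0 mL | about 12 mL |

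One more trough would give 18.0, 9.6 and 13.2 mL, above each maximum. Sample numbers also run without gaps (1–14, 100–106, 200–209). No row has been lost.

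**Step 2: which required days are never collected?** Required across both metrics: {7, 14, 21, 28, 42, 56}. Collected across all schedules: {7, 14, 28, 56, 84, 140, 168}. Never collected: {21, 42}.

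**Step 3: can visit windows supply them?** Protocol 8.3 allows ±3 days at weekly visits, so the Day 21 visit spans Days 18–24 and the Day 42 visit Days 39–45. A Day 14 sample falls no later than Day 17 and a Day 28 sample no earlier than Day 25. A Day 28 sample falls no later than Day 31 and a Day 56 sample no earlier than Day 53. Neither gap is filled.

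**Step 4: who is affected?** The Amendment 3 rationale reports 18 + 12 + 15 = 45 patients in Groups 1–3, so only Tables 8-5 and 8-7 apply. Day 21 alone blocks both metrics for everyone: 0 of 45 can have either from scheduled samples.

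**Step 5: what if available troughs are averaged?**

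| Metric | Extensive | Sparse | Days in common |
|---|---|---|---|
| Day 28, needs {7, 14, 21, 28} | {7, 14, 28}, 3 of 4 | {28}, 1 of 4 | 28 |
| Day 56, needs {7, 14, 21, 28, 42, 56} | {7, 14, 28}, 3 of 6 | {28, 56}, 2 of 6 | 28 |

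The planned minimum is 5 extensive patients in each of Groups 1–3, so at least 3 × 5 = 15 are extensive and at most 45 − 15 = 30 are sparse. The actual split is not given. If 15 to 25 were extensive (an assumption), 20 to 30 patients (44% to 67%) would have Day 28 as their only input to the Day 28 metric.

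As an illustration only, assume independent log-scale within-patient variation of equal size. The error SD of the sparse average relative to the extensive one is then √(3/1) = 1.73 for Day 28 and √(3/2) = 1.22 for Day 56. This does not measure bias in the odds ratio, and values below the LLOQ, which SAP 3.9 treats as missing for geometric means, would change the counts.

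**Step 6: who has no value?** Under SAP 3.5.3, patients who stop treatment before completing the Day 28 visit are non-responders. If sparse-sampled, they would usually have no scheduled concentration. They could enter the PK analysis set only through an unscheduled sample, a liver-injury work-up sample (Protocol 6.5.3.1) or a Day 28 visit sample drawn early in its window. Their number is not given.

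**The case against.** The strongest reply is that nothing important depends on this definition. The models are optional and no hypothesis is tested. The PK/PD endpoint is worded broadly, with AUC, Cmax and trough given only as examples. Dose intensity and population-PK exposure are open alternatives, and a separate plan, which may define the metric and the word adjusted, is foreseen. The no-imputation rule in SAP 3.9 can also be read as an instruction to take the geometric mean of the troughs that exist, in which case the metric can be calculated.

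Much of this stands, and it limits the weight of the point. It does not remove it. The alternatives are permitted but not specified, while the trough averages are stated as what the models will use. Reading SAP 3.9 as an averaging rule makes the metric computable only by letting it differ between schedules, and SAP 3.10 sets no minimum number of troughs. The separate plan is not among the documents, so it cannot be relied on or ruled out.

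A reader might infer more than the documents support:

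- That exposure-response cannot be analysed in this trial. It can: a population-PK analysis of all concentrations is already planned.
- That the sampling was deficient. The exposure-response text of Protocol 12.5.4 names no trough days; it is the SAP that departs from the schedule.
- That the efficacy results or the dose selection are in doubt. ORR and durable ORR use no concentration data, and RP2D selection rests on AUC and Cmax with review of safety and activity by the data monitoring committee.

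**Conclusion.** The mismatch is certain on the face of the two documents: Days 21 and 42 are required by SAP 3.10 and scheduled nowhere, so neither metric can be formed as written from scheduled samples. The schedule-dependence in Step 5 is conditional on averaging available troughs, which is a natural fallback but not a stated one. The link between having a Day 56 trough and having responded at Day 28 holds for sparse-sampled patients to the extent that the stopping rules are followed.

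Severity is minor to moderate. The effect is confined to optional models supporting one secondary objective. It still merits correction, because the study is open-label and leaving the covariate to be settled later invites a choice made with the responses in view.

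**What to change.** In SAP 3.10:

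- Delete Days 21 and 42, and define the word adjusted.
- Name one population-PK-derived exposure as the metric for both schedules.
- Average it over time on treatment only, up to the earlier of the last dose and the day before the assessment. Otherwise zero exposure after stopping for non-response would be counted as low exposure and would create a circular association.
- For the Day 56 model, use exposure up to Day 28, or state how patients who stopped at Day 28 are handled.
- Keep observed troughs on the scheduled days as descriptive summaries.
- Report how many patients, and how many responders, are excluded for lack of an evaluable concentration.

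If a separate plan already defines the metric, cite it and remove the uncollected days.

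The cost is a rewritten paragraph in SAP 3.10 and a small table of exclusions. The protocol, the sampling and the PK analysis set do not change, and the population-PK work is already planned. The downside is that the metric depends on the population-PK model, to which sparse-sampled patients contribute few samples.

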6.1.5 Treatment duration

The planned duration of aGvHD treatment is 24 weeks (approximately 6 months).

The Treatment Period for each patient will begin on Study Day 1 and continue until the end of Week 24, unless treatment change for any reason including treatment failure, e.g. aGvHD progression, mixed response, or no response, or aGvHD flare failure as defined in [Section 8.4.1.2](#), intolerable toxicity, death, or withdrawal from the study for other reasons occurs.

During the Treatment period, and beyond Day 28, patient's treatment will be managed according to their response as follows:

For patients with response at Day 28 (see [Table 8-3](#)):

- Patients responding to ruxolitinib will continue ruxolitinib until Day 56. These patients may be tapered off ruxolitinib as needed, starting no earlier than Day 56. The dose tapering strategy should be based on evaluation of the condition of the subject, current dosing regimen and the clinical judgment of the Investigator. (see [Section 6.1.5.1](#).)
- If a taper of ruxolitinib is considered appropriate, the taper should be completed no later than Week 24 unless prolonged tapering is indicated due to an aGvHD flare or other safety concern (see [Section 6.1.5.1](#)).

For patients with a lack of response at Day 28 (see [Table 8-3](#)):

- Patients must discontinue study treatment and be treated per Investigator's judgement. These patients will then enter the long-term follow-up period.

Patients responding to treatment will be tapered off immunosuppression (corticosteroids and CNI) as described in [Section 6.1.5.1](#).

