3.5.3 Handling of missing values/censoring/discontinuations

Patients with missing assessments that prevent the evaluation of the ORR will be considered non-responders. This includes aGvHD response assessments at baseline and Days 28, 56. Patients who discontinue the study treatment prior to the completion of the Day 28 visit will be considered non-responders.

The following analysis windows will be applied to the target day for assessments on overall response, where target day for Week X is X*7.

Baseline assessment is the last aGvHD assessment prior to or at the start of study treatment (Day 1).

Weeks 1, 2, 3, 4, 5, 6, 7, 8: -3 days/+3 days

Weeks 12 to 48: -13 days/+14 days

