3.6 Analysis of the key secondary objective

3.6.1 Key secondary endpoint

The key secondary objective of the study is durable ORR at Day 56.

Durable ORR at Day 56 is defined as the proportions of all patients who achieve a complete response (CR) or partial response (PR) at Day 28 and maintain a CR or PR at Day 56. If a patient is a CR at Day 28 and a PR at Day 56, he/she will be considered as a durable responder. A patient will not be considered a durable responder at Day 56 if any of the following events occurs:

- Not responder at Day 28
- Missing aGvHD assessment at Day 56
- No CR or PR at Day 56.
- additional systemic therapy for aGvHD prior to Day 56

Durable ORR will be calculated based on the FAS using local investigators review of aGvHD assessment data.

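### The Day 56 exposure-response model averages exposure over a window whose length depends on the Day 28 outcome, so its odds ratio can be biased in either direction

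*SAP*

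**What the plan says.** SAP 3.10 proposes that "logistic regression models for efficacy may be used including log- time-averaged trough concentration". For the Day 28 response the covariate is the "geometric mean of the Day 7, Day 14, Day 21 and Day 28 adjusted trough concentration". For durable response at Day 56, "A similar average trough concentration will be calculated for the Day 56 response except the Day 42 and Day 56 will also be included". The result is an odds ratio with a 95% interval for a doubling of exposure. Two alternatives are left open. One is that "other exposure measures (such as dose intensity) may be considered if appropriate". The other is population-PK exposure, "computed by the population PK model accounting for dose modifications or dose interruptions up to the day prior to the day of assessments".

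Three rules elsewhere bear on this:

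- Protocol 6.1.5 says of patients without a response at Day 28: "Patients must discontinue study treatment and be treated per" the investigator's discretion. Protocol 9.1.1 lists the same condition as a required reason to stop. Responders stay on ruxolitinib to Day 56.
- SAP 3.6.1 lists "Not responder at Day 28" among the conditions that rule out durable response.
- For the Day 28 endpoint, SAP 3.5.3 says: "Patients who discontinue the study treatment prior to the completion of the Day 28 visit will be considered non-responders".

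SAP 3.10 sets no landmark time, does not restrict the Day 56 model to Day 28 responders, and gives no rule for time off drug.

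**The concern.** Non-response at Day 28 does two things at once. It fixes the Day 56 outcome as non-durable, and it ends the treatment whose level is being averaged. The covariate is therefore partly a consequence of the outcome, and the odds ratio need not be 1 when exposure has no effect.

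PK/PD relationships are a listed secondary objective (Protocol Table 2-1), and Protocol 4.2 assumes that exposure drives efficacy. An odds ratio produced by the stopping rule could be read as support for that assumption. A bias in the other direction could be read as evidence against it.

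**Working it through.** **The plan's own figure.** The SAP gives no operating characteristics for this model. Its related figure is for N = 45 and a true ORR of 80%: P(X ≥ 33) = 0.9005, against 0.901 in SAP Table 4-1. The 90% Clopper-Pearson interval for 33/45 is 0.604 to 0.838; 32/45 has a lower limit of 0.580. The figure reproduces, and N = 45 and 80% are used below.

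**Do off-drug troughs enter the average?** SAP 3.9 treats values below the quantification limit as missing for geometric means and does not impute missing PK data. SAP 3.2 accepts a concentration only if ruxolitinib was taken before the sample. Inputs from the protocol are a target AUC0-12 of 539 ng·h/mL (4.2), half-life 2.3 to 3 h (1.1.2.1.2) and a limit of about 0.5 ng/mL (8.6.1.2).

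- Approximate trough = AUC·k·e^(-12k)/(1 - e^(-12k)), with k = ln 2 / half-life. This gives 4.5 ng/mL (2.3 h) and 8.3 ng/mL (3 h).
- Time to fall below 0.5 = half-life × log2(trough/0.5), or 7.3 h and 12.2 h after the missed dose.

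A patient who stops at Day 28 without a taper is unquantifiable by Day 42, and the later values drop out.

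**How far each handling shifts the average.** Four of the six listed troughs fall by Day 28.

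- Off-drug values dropped, continuing patients' later troughs multiplied by f: their average shifts by f^(2/6). For f = 0.75, 0.5 and 1.25 this is 0.91, 0.79 and 1.08.
- Non-responders on a half-dose taper at Days 42 and 56: their average shifts by 0.5^(2/6) = 0.79.
- Off-drug time counted as zero in an arithmetic average: non-responders shift by 4/6 = 0.67 (weighted by sample) or 28/55 = 0.51 (weighted by day).

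**Simulation with no exposure effect.** N = 45 and Day 28 response 80%. Durable response among Day 28 responders is 64% (61/96 in the Phase III ruxolitinib arm, Protocol 1.1.2.1.2) or 90% (assumed). Between-patient log SD = sqrt(ln(1 + 0.557²)) = 0.52, which is the protocol's Cmax CV assumed to hold for troughs. Within-patient log SD is 0.3 (assumed; 0.2 and 0.5 made little difference where tried). Durable response is regressed on log2 average exposure, with a likelihood-ratio test at 5%. Cells show median odds ratio per doubling, then rejection rate.

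| Handling after Day 28 | 64% durable | 90% durable |
|---|---|---|
| Off-drug dropped, no drift | 1.01, 5.3% | 1.00, 5.4% |
| Off-drug dropped, on-drug -25% | 0.92, 6.1% | 0.84, 7.6% |
| Off-drug dropped, on-drug -50% | 0.79, 10.0% | 0.65, 17.0% |
| Off-drug dropped, on-drug +25% | 1.09, 5.8% | 1.15, 6.6% |
| Non-responders on half-dose taper | 1.27, 9.8% | 1.53, 15.6% |
| Off-drug = 0, weighted by sample | 1.50, 17.5% | 2.06, 37.2% |
| Window ends at Day 28, all patients | 1.01, 5.4% | 0.99, 5.2% |
| Day 28 responders only, to Day 56 | 1.00, 6.3% | 1.01, 5.2% |

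With off-drug time as zero and weighting by day (28/55), rejection is 37% and 73% in the same two columns. At Day 28 response/durable rates of 62%/65%, 70%/75% and 80%/80% it is 69%, 68% and 55%.

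The responders-only row is optimistic. Patients who start new systemic therapy between Days 28 and 56 must also stop ruxolitinib (Protocol 9.1.1) and are also durable non-responders. If half of the non-durable responders stop at Day 42 (assumed), that model rejects in about 10% to 13%.

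**Sampling.** Protocol Tables 8-5 to 8-7 schedule no Day 21 or Day 42 trough. Extensive-PK and Group 4 patients have pre-dose samples on Days 7, 14 and 28 (three of the six). Sparse-PK patients have Days 28 and 56 (two of the six). The listed average cannot be formed in full from scheduled samples, which makes the population-PK route more likely to be used.

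**The case against.** The strongest reply is that the metric actually specified is a geometric mean of observed troughs. Under the SAP's rules off-drug values are removed, not set to zero, and the simulation then shows no artefact: odds ratio 1.01 or 1.00, with much the same result on the real sampling schedule. That stands. A reader might infer that a positive exposure effect is built into the Day 56 model; the documents do not support this for observed troughs.

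Other parts of the reply also stand. Dose intensity as defined in SAP 3.4.1 divides by the time from first to last dose, so it leaves out time after stopping. The population-PK route is optional, and nothing says that off-drug days must be averaged in. The models themselves are optional, further detail may come in a separate plan, and no efficacy hypothesis is tested. The rejection rates above are best read as roughly how often the reported 95% interval would exclude 1.

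The reply does not close the point, for three reasons. Dropping off-drug values leaves unequal windows. SAP 3.10 neither says that the 3.9 rules govern a per-patient covariate nor defines *adjusted* trough. And the population-PK wording, together with the optional taper on discontinuation in Protocol 6.5.2.1.3, leaves open the routes by which low exposure after Day 28 can enter.

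**Conclusion.** The exposure window in the Day 56 model depends on the outcome. The direction of the resulting bias depends on choices that the SAP leaves open.

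- Observed troughs, off-drug values dropped: no bias if on-drug troughs are stable after Day 28. Otherwise the null odds ratio runs from about 0.65 to 1.15 for assumed average drifts of -50% to +25%. Table 6-4 reductions are 50%, so an average fall of 25% corresponds to half the continuing patients on a halved dose (0.5 × 1 + 0.5 × 0.5 = 0.75). A 50% average fall is an extreme case.
- Model-derived exposure with off-drug time as zero: positive bias, with about 18% to 75% rejection at nominal 5%, depending on weighting and response rates.
- Half-dose taper after the decision to stop: positive bias, with about 10% to 16% rejection.

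These sizes rest on the assumed within-patient SD, the Cmax CV applied to troughs, the drift sizes and the durable-response rates.

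Two further inferences would go too far. The first is that the Day 28 model shares the fault: for observed troughs early stoppers contribute fewer values, not off-drug values, so the issue largely disappears unless population-PK exposure counts off-drug days. The second is that the efficacy results are affected: primary ORR and durable ORR do not use this covariate. The point is worth correcting because PK/PD is a stated secondary objective and the change is small.

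**What to change.** In SAP 3.10 and any separate exposure-response plan:

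1. Delete the clause that adds Day 42 and Day 56. Use exposure up to Day 28, on-drug time only, as the covariate for Day 56 durable response in all EES patients with PK data.
2. If population-PK exposure is used for the Day 28 or the Day 56 model, end it at the earlier of the last dose or the day before the Day 28 assessment.
3. Make any model of Day 28 to 56 exposure among Day 28 responders secondary, with exposure cut at the start of new systemic therapy or at the last dose.
4. State that the SAP 3.9 and PAS rules apply to this covariate, define *adjusted* trough, and align the listed days with the sampling tables.

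The cost is document wording only; no new data are needed. Exposure between Days 28 and 56 no longer enters the all-patient model. Sparse-PK patients have only the Day 28 scheduled trough inside the shorter window, so model-derived exposure may be needed for them, under the limit in item 2.
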